Additional studies have been initiated or planned using NR to study effects on mitochondrial biology related conditions including aging (at the University of Colorado in Boulder – actively recruiting) and in heart failure (University of Washington in Seattle – protocol in developmental stage). Based on blood levels of NAD⁺ from a pilot study performed at the University of Iowa, the dose of NR chosen by aging and heart failure studies is 1 gram daily. The PI ([name]) has also discussed the experience to date with Drs [name] (UC – Boulder) and [name] (U. of Washington). As of May 17, 2016 the Boulder team has enrolled 20 subjects of whom 10 subjects had been taking 1 gram of NR daily with no evidence of intolerance or side effects. The Seattle team has completed a pharmacokinetics study (NCT02689882) on 8 subjects taking incremental doses up to 1 gram bid up to 9 days. This study revealed no significant side effects and enrollment of the first subject on the heart failure study had been initiated. We therefore propose to use the 1 gram daily dose.

3. Hypothesis

Nicotinamide riboside, as a Sirt3 activator, will mimic the beneficial immune effects of prolonged fasting and suppress immune activation of refeeding.

Proposed Scientific/Clinical Innovations and Advances of the Study

- Evaluate whether pharmacologic activation of Sirt3, via enhancing mitochondrial integrity will blunt sterile-inflammation linked NLRP3 inflammasome activation.
- Expand our understanding how NR can modulate the regulation of additional innate and adaptive immune pathways

[figure not shown]
4. Objectives

- 1. Explore whether NR administration will blunt NLRP3 activation in human subjects.
- 2. Explore whether NR will modulate additional innate (NK cell) and adaptive (T-cell) immune programs.
- 3. Employ proteomic and cytokine array analysis to obtain a broader understanding of the NR mediated effects on mitochondrial biology in modulating immune regulation in circulating cells and in the serum of study subjects.

5. Study Design and Procedures

The study design is a prospective, double-blind randomized crossover study with subjects serving as their own controls.

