Normal volunteers will be enrolled on this 3-5 week study that includes 3 visits to the NIH Clinical Center. Subjects may be contacted by telephone, text or email to verify study compound compliance, for AE/safety assessment and to remind subjects to initiate the 24-hour fast prior to Visit #2 and Visit #3. Email communications will be made through the NIH medical secure email system unless the patient declines its' use and requests standard unsecure email. A schematic showing the outline of the overall study is shown below.

The variable length of the washout and study arms phase is to allow flexibility for the scheduling of subject visits. The prior pharmacokinetic studies support that 7 days is more than sufficient to restore NAD⁺ levels to baseline.

The following actions will be undertaken at the defined visits:

Arm 1

Screening/Visit 1:

- Subjects will be screened for inclusion or exclusion.
- Baseline screening laboratories performed.
- Pregnancy testing in women of childbearing potential.

- Eligible subjects will be randomized to placebo (i.e. sugar tablet) or 1 gram of NR daily. The study compound start date will be determined at this visit. Start date will be within one week of screening visit.
- Instruct subject on study compound administration, reinforce maintenance of stable diet and activity level during the study participation period, and review the time of the breakfast on day 6 (+3 days, if needed), prior to initiating the 24-hour fast.

Day 1 of Arm 1 study compound administration.

A member of the research team may contact study subjects:

- to remind them which day to initiate therapy
- to remind subjects of the 24-hour \pm 2hr fast

Visit 2: Day 7 (+ up to 3 days, if needed) of Arm 1 study compound administration

- Subjects will arrive at the Clinical Center after a 24-hour fast ± 2 hours with the
 exception of drinking water starting the morning of day 6 (+ up to 3 days, if
 needed).
- A pill count will be performed to evaluate compliance.
- Fasting blood draw for hepatic panel, acute care panel, insulin, growth hormone, complete blood count, serum immune cell studies and to measure NAD levels.
- Urine collection for ketones
- Administer day 7 (+ up to 3 days, if needed) Arm 1 placebo/NR capsules.
- A 500 caloric meal will be eaten.
- Refed blood-draw for insulin, growth hormone, glucose, serum immune cell studies and to measure NAD levels three hours ± 30 minutes after fixed caloric meal (metabolic kitchen).

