The pharmacist Co-Investigator on the study will devise a randomization code in consultation with [name] (Biostatistician). This code will be kept confidential and will be employed by the pharmacy to dispense the study pills. For each arm, subjects would receive sufficient pills for 7 days of administration. If additional pills are needed to extend the treatment arm by up to three days, these will be dispensed separately by the pharmacy. Subjects will take their study medication at home for days 1 through 6 (+ up to 3 days, if needed). Day 7 (+ up to 3 days, if needed) dosing will be in the clinic. Subjects will be instructed to bring their study medication bottle back to the clinical center for day 7 (+ up to 3 days, if needed) dosing and to not take the day 7 (+ up to 3 days, if needed) dose until instructed to by the study team. If the subject forgets to bring the study bottle with the day 7 (+ up to 3 days, if needed) dose, the day 7 (+ up to 3 days, if needed) dose will be ordered through CRIS from the pharmacy. A process has been developed by the NHLBI pharmacist to ensure the subject receives the correct study compound or placebo. The day 7 (+ up to 3 days, if needed) pill for each arm will be given to the study subject for consumption following the 24-hour fasting research blood draw. The study pill receptacle will have the subject's name, code number, prescription details (4 tablets by mouth each morning with or without food) and will include the arm (1 or 2). If the study subject does not bring in the pill bottle, the subject will be asked to confirm the number of study doses taken over the prior 6 (+ up

Amendment F, May 22, 2018 [name], PhD to 3 days, if needed) days and this will be documented in the medical record. The pill bottles will then either be collected at the next visit or we will have the subject return by FedEx. The code will be shared with the statistician following the completion of studies on 20 subjects to evaluate observed standard deviations to assess original study assumptions and continued study feasibility.

Description of Study Population and Recruitment

Participants will be enrolled at the NIH Clinical Center. Subjects will be recruited through a LISTSERV email announcement and study procedures will be performed in the outpatient unit/day hospital at the NIH Clinical Center. A list of healthy volunteers may also be requested from the NIH Office of Patient Recruitment.

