A total of 42 participants will be recruited for this study.

6. Eligibility Assessment

The PI and/or AI will assess eligibility. Screening will be performed under this protocol only. Screening studies for subject enrollment:

- i. History and physical examination.
- ii. Screening and Research laboratory tests may include:
 - o Acute Care Panel (Na, K, Cl, CO2, Creatinine, Glucose, and Urea Nitrogen)
 - o Mineral Panel (Phosphorus, Magnesium, Albumin, and Calcium)
 - o Hepatic Panel (Alk Phosphatase, ALT, AST, Total Bilirubin, and Direct Bilirubin)
 - CBC + Differential
 - o Blood draw for immune cell studies and NAD levels
 - o Urine for ketones
 - o Growth hormone o

Insulin level

- o Glucose
- o βHCG (females of childbearing potential)

Inclusion Criteria

As this is a pilot study, the age-range and BMI range of subjects will be restricted to potentially reduce metabolic variables associated with a wide age- and BMI-range.

- Males and females between the ages of 18 and 39
- BMI between 18.5 and 29.9
- Agrees to comply with study procedures and maintain current level of physical activity and dietary intake throughout the study.
- Female subjects of child-bearing ability willing to commit to reliable contraception while participating in the study.

Exclusion Criteria

- Subjects with an acute or chronic illness as per history, on laboratory analysis or requiring medications to manage disease.
- Subjects taking vitamins or supplements or any medications, except oral contraceptives, within 4 weeks of participation into this study.
- BMI <18.5 or >29.9.
- Female subjects who are pregnant or lactating.
- Subjects who have donated blood or participated in another clinical trial involving blood draws in the last 8 weeks.
- Subjects who use nicotine products including chewing tobacco, vaporizer, gum, cigarette or patch form within three months.
- Any other medical condition that, in the opinion of the Principal Investigator, might put the subject at risk of harm during the study or might adversely affect the interpretation of the study data.

7. Procedures

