All tests will follow NIH Clinical Center policies. Any of the listed procedures or laboratory tests performed within three months prior to enrollment in this protocol may/may not be repeated. However, if these procedures are not repeated, the prior studies (within the last 3 months) will be reviewed in CRIS as part of the protocol. The purpose for not repeating study procedures is to prevent unnecessary inconveniences, risks or discomforts for study participants and the NIH Clinical Center.

- *i)* **Blood Draws:** In addition to the screening blood draw (40 mL), subjects will have 4 additional research blood draws up to 100 mL each, as described in Section 4.
- *ii) Urine Analysis:* Subjects will be asked to provide up to three urine samples, one for pregnancy testing as part of screening evaluation and two in the fasting state at Visits 2 and 3 as described in Section 4.
- *iii)* 24-Hour Fasting: Subjects will be asked to fast for up to 26 hours (water intake will not be restricted) during each of the two treatment arms.
- *iv) Fixed Caloric Meal:* The meal will be a 500 calorie breakfast. Subjects will have a choice of two meals.

| Meal Choices | Description of Meal | | | | |
|--------------|---|--|--|--|--|
| Option 1 | Vegetable omelet | | | | |
| | Toast with butter and jelly | | | | |
| | Orange juice | | | | |
| Option 2 - | Oatmeal with Walnuts, Brown Sugar and Dried | | | | |
| | Cranberries | | | | |
| | • Milk | | | | |

8. Dietary Supplement

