We propose that NR functions as a fasting mimetic and we will assess whether after refeeding the NLRP3 inflammasome activation (IL-1\beta release) is blunted by NR as the primary endpoint. In our prior study, the mean±SD value of fasting IL-1β release was 319±513 pg/ml, while the mean refed value was 736±1067 pg/ml (with 417±613 pg/ml for the paired refed-fasting IL-1β release differences). In this placebo-controlled crossover study, we would like to detect a relative reduction of at least 20% in refeeding IL-1β release (from 736 to 589 pg/ml) with NR treatment compared to the paired responses on placebo. The crossover design has the benefit of reducing the influence of confounding covariates (because each subject serves as their own control) and is statistically efficient, requiring fewer subjects than non-crossover designs. Since estimates of within-subject variability for both the NR and placebo arms, between-subject variability for the NR arm, and between-subject covariance between NR and placebo are not available for this novel exploratory study, the usual crossover study sample size formulas cannot be used. Instead, we calculate sample size using the paired Student t-test. With a standard deviation of 276 pg/ml (45%) of that observed for the fasting-refed differences), 80% power and an alpha=0.05, we will need 30 subjects to detect a 20% relative decrease (absolute decrease of 147 pg/dl from 736 to 589 pg/dl) for the paired treatment differences in IL-1β release with NR treatment. We therefore request approval to enroll up to 35 normal volunteers to account for possible treatment non-compliance and /or study dropouts.

There will be no interim efficacy look at the data in this proof-of-concept study. However, when 20 subjects have completed the study, the protocol statistician will perform a sample size re-

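### Subjects choose between two different 500-calorie refeeding meals and nothing keeps the choice the same at Visits 2 and 3; repeating it is a cheap precaution whose gain in precision is small and may be zero

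*Combined protocol and SAP*

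**What the plan says.** Section 5 describes a "prospective, double-blind randomized crossover study with subjects serving as their own controls". At Visits 2 and 3 the subject arrives after a 24-hour fast, gives a fasting sample, eats a test meal, and gives a refed sample three hours (± 30 minutes) later. Section 10 (Primary study outcome) compares refed IL-1β secretion on NR with the same subject's value on placebo, by the Wilcoxon signed rank test.

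Section 7 iv sets the meal at 500 calories and adds: "Subjects will have a choice of two meals". Option 1 is a vegetable omelet, toast with butter and jelly, and orange juice. Option 2 is oatmeal with walnuts, brown sugar and dried cranberries, and milk. The Visit 2 and Visit 3 lists in Section 5 each say only "A 500 caloric meal will be eaten".

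Two passages ask for stability of diet. At Visit 1 staff are to "reinforce maintenance of stable diet and activity level during the study participation period", and an inclusion criterion in Section 6 has subjects agree to "maintain current level of physical activity and dietary intake throughout the study". Neither names the test meal. Section 6 also explains that age and BMI are "restricted to potentially reduce metabolic variables associated with a wide age- and BMI-range".

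**The concern.** The meal is the stimulus whose effect the primary endpoint measures. The crossover gains its efficiency by holding everything but treatment constant within a subject, and the plan narrows age and BMI to remove metabolic variation. Yet the composition of the stimulus may differ between a subject's two periods. If the two meals provoke different IL-1β responses, every subject who switches carries that difference into the NR-minus-placebo contrast. The fasting sample precedes the meal, so subtracting it does not remove the effect. If the option is not recorded, nobody can later check whether the two challenges matched. What is at stake is precision in a small paired trial.

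**Working it through.** **Inputs from Section 10.**
- Initial planning, on the refed difference between treatments: "With a standard deviation of 276 pg/ml" (45% of 613), difference 147 pg/ml (736 to 589), 80% power, n = 30.
- Recalculation of October 2017, on fed-minus-fasting differences between treatments: observed SD 177.002 pg/ml from 17 evaluable subjects, difference 83 pg/ml (20% of 417 = 83.4), two-sided alpha 0.05, n = 36.

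**Reproducing the plan's sample sizes.**
- Initial: the paired t-test with the noncentral t distribution gives n = 30.
- Recalculation: the normal approximation gives (2.8016 × 177.002 / 83.4)² = 35.4, so n = 36. The paired t-test gives 38, and at n = 36 its power is 78.5%. That is the starting value below.

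**Model for switching.** Let p be the share of subjects who switch option and d the additive difference in refed IL-1β between the meals. Treatment order is randomized and blinded, so a switcher's paired difference gains +d or −d with equal chance. The mean is unchanged and the variance gains p × d². Because the meal affects only the refed sample, the same term applies to the refed difference and to the fed-minus-fasting difference.

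**Assumptions.** The documents give neither p nor d. I take p = 10%, 25% and 50%, and d = 41.7 and 83.4 pg/ml (10% and 20% of the 417 pg/ml refeeding response). If p or d is zero, nothing changes.

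**How many subjects can still benefit.** Seventeen were already evaluable in October 2017, and the current text is dated "Amendment F, May 22, 2018". At most 36 − 17 = 19 of 36 can be affected by a change now. The documents do not say how many remain, so 19 is an upper bound.

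**Is switching already inside the SD of 177?** The chance of no switcher among 17 is 0.50¹⁷ = 0.0000076 at 50% switching, 0.75¹⁷ = 0.0075 at 25%, and 0.90¹⁷ = 0.167 at 10%. At 25-50% the observed SD almost certainly contains some switching. At 10% this is less certain, but the amounts there are small.

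**Recalculation basis** (difference 83.4, n = 36). With the meal repeated for 19 of 36, SD = √(177.002² − (19/36) × p × d²). **Refed planning basis** at the current n = 36 (difference 147). With switching added, SD = √(276² + p × d²). Without switching its power is 87.4%.

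| p | d (pg/ml) | p × d² | Share of 177.002² | SD, 19 of 36 repeat | Power (from 78.5%) | SD on 276 basis | Power (from 87.4%) |
|---|---|---|---|---|---|---|---|
| 10% | 41.7 | 173.9 | 0.6% | 176.7 | 78.6% | 276.3 | 87.4% |
| 10% | 83.4 | 695.6 | 2.2% | 176.0 | 79.0% | 277.3 | 87.1% |
| 25% | 41.7 | 434.7 | 1.4% | 176.4 | 78.8% | 276.8 | 87.2% |
| 25% | 83.4 | 1738.9 | 5.6% | 174.4 | 79.7% | 279.1 | 86.7% |
| 50% | 41.7 | 869.4 | 2.8% | 175.7 | 79.1% | 277.6 | 87.1% |
| 50% | 83.4 | 3477.8 | 11.1% | 171.7 | 80.9% | 282.2 | 86.0% |

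**Check on bias.** Simulating the Wilcoxon signed rank test under no treatment effect, with half the subjects switching at random and meal differences of 50-200 pg/ml, gave type I error of 4.5-5.3% (8,000 runs per scenario). Balanced switching costs power, not validity.

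**Check on the additive assumption.** Suppose the meal effect is d under placebo and d + i under NR, and the options are equally popular. The meal-related variance of the paired difference is then i²/4 + p × d × (d + i); repeating the meal removes the second term. That term is negative only if d and d + i have opposite signs, that is, if NR reverses the direction of the meal effect. Only then would repeating the meal cost precision.

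**The case against.** The strongest reply is that no defect is demonstrated. The documents do not show that the meals differ in their effect on IL-1β or that anyone switches, and the upper meal difference used above equals the whole treatment effect in the recalculation. Calories are fixed, the meal comes from the metabolic kitchen, subjects agree to keep their diet stable, and this is a pilot. The choice of two meals could also be read as one choice per subject, and the site may already repeat the meal. The recalculation figures, moreover, concern fed-minus-fasting differences, while the stated primary outcome is refed secretion.

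Most of this limits the size of the point. The inputs are assumptions and zero is possible. The primary-outcome basis belongs at the current n = 36, where power stays near 86% or above throughout; the initial n = 30 would make the loss look more consequential than it is. None of it closes the gap. Equal calories are not the same food, the diet wording does not reach the test meal, and the text does not settle whether the choice is made once or at each visit.

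The change is not wholly free either. Section 12 sends every amendment to the IRB and requires deviations, including non-serious ones, to be reported. A subject who refused the same breakfast would create one.

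**Conclusion.** The point holds as a small precision improvement. The plan permits a different refeeding stimulus under NR than under placebo in the comparison that decides the primary outcome, and repeating the option removes that source of noise at little cost. Under the stated assumptions the gain is 0.1 to 2.4 percentage points of power on the recalculation basis (78.5% to 78.6-80.9%). On the refed planning basis the loss from switching is at most about 1.4 points (87.4% to 86.0%). With no switching or no meal difference it is zero.

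A reader might infer more, and the documents do not support it:
- *That the comparison is biased.* Order is randomized and blinded, and nothing links meal choice to treatment.
- *That the sample size is too small because of switching.* The SD of 177 was observed under the same free choice, so it probably includes switching already, though this is less sure at 10%.
- *That repeating the meal would raise power to as much as 83.0%.* That figure requires repetition in all 36 subjects, and at least 17 were past that point.
- *That repeating the meal can only help.* This is exact for an additive meal effect; a reversal of the meal effect under NR would break it, though nothing in the documents suggests one.

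**What to change.** Add to Section 7 iv: *The meal option eaten at Visit 2 will be repeated at Visit 3, and the option will be recorded.* No change to the sample size or the analysis is needed.

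The cost is a minor amendment with IRB approval, one recorded field, and the subject's free choice at Visit 3; the first choice stays with the subject, and a refusal at Visit 3 would count as a minor deviation. There are no added visits, blood draws or subjects. The change helps only those who have not yet completed Visit 3. For the others, the options eaten can be tabulated if the site has a record of them.

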calculation using only the observed standard deviation of the paired between treatment IL-1β changes to assess the original study assumptions and continued study feasibility. The study PI will remain blinded to the primary outcomes. The study will be judged feasible jointly by the study PI and Statistician if the new sample size calculation shows that 50 or fewer subjects can answer the primary hypothesis concerning IL-1β. If the study is feasible and continues, the sample size will not be reduced below the originally calculated requirement of 30 but, if needed, a request for a new larger enrollment ceiling (not to exceed 58 subjects, accounting for study drop-outs and non-adherers) will be presented to the IRB for consideration.

Of note, the sample size recalculation was performed on October 19th, 2017 after the enrollment of 20 subjects. The study sample size was recalculated using an updated observed standard deviation of the between treatment fed-fasting differences in IL-1beta levels (S = 177.002 pg/ml) based on 17/20 evaluable subjects enrolled into the protocol. The new calculation was performed for fed-fasting differences rather than fed differences between treatments (a more conservative approach) to allow adjustment for any differences in baseline fasting IL-1beta levels between study periods. With an observed standard deviation of 177 pg/ml, 80% power, and a two-sided alpha=0.05, we will need n=36 subjects to detect a 20% relative decrease (absolute decrease of 83 pg/ml from the protocol-specified mean level of 417 pg/ml to 333 pg/ml) for the paired fed-fasting differences between treatments in IL-1beta release with NR treatment. As the study continues to be feasible (requires the enrollment of fewer than 50 subjects), we request approval to continue enrolling up to 42 normal volunteers to account for possible treatment non-compliance and/or study dropouts.

Primary study outcome:

The primary study outcome will be the refeeding IL-1 β secretion in response to inflammasome stimulation in the NR treatment arm versus the same subject's response on the placebo treatment arm using the nonparametric Wilcoxon Signed Rank test.

Additional Analyses:

- NLRP3 inflammasome activation in PBMC's (IL-1β in the fasting state)
- Isolate PBMC's to explore mitochondrial functioning and biochemistry (oxygen consumption rate in leukocytes)

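### The recalculated n=36 with 80% power is for fed-minus-fasting IL-1β, not for the declared primary outcome (refed IL-1β), whose power and 50-subject feasibility check are therefore not established

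*Combined protocol and SAP*

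**What the plan says.** All of this is in Section 10 (Statistical Considerations) unless noted.

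- **Planned target.** The primary endpoint is IL-1β release after refeeding: "we would like to detect a relative reduction of at least 20% in refeeding" IL-1β release, from 736 to 589 pg/ml. This is a drop of 147 (printed once in pg/dl; I read pg/ml). The paired t-test with an assumed SD of 276 gives n=30 at 80% power. The variance components were not available at planning, so "the usual crossover study sample size formulas cannot be used".
- **Rule for the recalculation.** After 20 completers, the statistician updates the sample size from the observed SD alone. The study is feasible if "50 or fewer subjects can answer the primary hypothesis" on IL-1β.
- **What was done.** "The new calculation was performed for fed-fasting differences rather than fed differences between treatments (a more conservative approach", in the plan's words. The stated reason is adjustment for differences between periods in what it calls baseline fasting IL-1β. The SD was 177.002 pg/ml from 17 evaluable subjects, the target was an "absolute decrease of 83 pg/ml from the protocol-specified mean level of 417 pg/ml to 333 pg/ml", and the result was n=36. The study was declared feasible, with enrolment up to 42.
- **Primary outcome after the recalculation.** "The primary study outcome will be the refeeding" IL-1β secretion on NR against the same subject's value on placebo, tested by Wilcoxon signed rank. Fed-minus-fasting IL-1β appears neither here nor under Additional Analyses.
- **Timing of the fasting sample** (Section 5, Randomization and dispensing of study pills). "Subjects will take their study medication at home for days 1 through 6", plus up to three more days if needed. The day 7 dose is given "for consumption following the 24-hour fasting research blood draw".

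**The concern.** A reader, or the IRB, will take 80% at n=36 as the power of the primary test. It is the power of a different contrast, with its own target (83 rather than 147) and its own SD (177). Three statements depend on a number that is not printed, the SD of the NR-placebo difference in refed IL-1β:

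- the power of the primary test;
- the conclusion that no more than 50 subjects are needed for the primary hypothesis;
- the claim that the switch was conservative.

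The reason given for the switch also needs correcting. The fasting sample follows at least six days of NR or placebo, so it is an on-treatment value and not a baseline. Subtracting it could remove part of any NR effect already present in the fasted state.

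**Working it through.** **Inputs (Section 10).** Planned: δ = 147, SD = 276, n = 30. Recalculated: δ = 83, SD = 177.002, n = 36. Power 80%, α = 0.05, two-sided. The planning text does not state sidedness, but two-sided reproduces its n.

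**Formulas.** Normal approximation: n = [(z₀.₉₇₅ + z₀.₈₀) × SD/δ]², with 1.960 + 0.842 = 2.802. Exact paired t: noncentral t on n − 1 df with noncentrality (δ/SD)√n.

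**1. The plan's own figures**

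- 147/276: exact paired t gives n = 30 (power 80.5%), as stated. The normal approximation would give 28.
- 83/177.002: (2.802 × 177.002/83)² = 35.7, so 36, as stated. The exact paired t gives 38, and its power at 36 is 78.1%.

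So 36 is correct for the contrast sized, but by the normal approximation rather than the exact method that reproduces the planned 30. The difference is minor, and 38 is still below the ceiling of 42.

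**2. Why 177 cannot stand in for the missing SD**

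Within a subject, the NR-placebo difference in refed IL-1β equals the NR-placebo difference in fed-minus-fasting plus the NR-placebo difference in fasting. Hence SD²(refed) = 177² + SD²(fasting) + 2 × covariance. The result can lie above or below 177. For example, if the two parts are uncorrelated, an SD of 306 is reached when the fasting-difference SD is √(306² − 177²) ≈ 250.

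**3. Power of the declared primary contrast at n = 36, δ = 147 (the SD is an assumption)**

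| SD of refed difference | Noncentrality 147 × 6/SD | Power, paired t | n for 80% |
|---|---|---|---|
| 250 | 3.53 | 93% | 25 |
| 276 | 3.20 | 87% | 30 |
| 306 | 2.88 | 80% | 36 |
| 350 | 2.52 | 69% | 47 |
| 400 | 2.21 | 57% | 61 |

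The declared Wilcoxon test, in 20,000 simulated normal trials at n = 36, gives 86% at SD 276, 79% at 306 and 67% at 350.

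**4. Thresholds**

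- 36 subjects give 80% power only if the SD is about 306 or less.
- The 50-subject limit holds up to an SD of about 363. At n = 50, power is 80.2% at SD 363 and 79.9% at 364. With 20% of 736 left unrounded at 147.2, the limit is about 364.
- The switch is conservative only if 147/SD exceeds 83/177.002, that is, if SD < 147 × 177.002/83 = 313.5 (312.4 with unrounded 147.2 and 83.4). This exceeds 306 because 36 subjects give only 78% for the contrast sized.

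**5. Precision of an SD from 17 subjects**

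On 16 df, the 95% limits are √(16/χ²) = 0.745 and 1.522 times the estimate, if the data are normal. For the reported 177 that is about 132 to 269.

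**The case against.** The switch is disclosed, with a reason. The recalculation rule speaks of between-treatment IL-1β changes without defining changes, so fed-minus-fasting may be what was meant. The two targets can also describe one effect: a uniform 20% cut takes 319 to 255.2 and 736 to 588.8, so the difference goes from 417 to 333.6. The planning calculation already supports the primary outcome at SD 276, and 36 exceeds its 30. Finally, the statistician could compute both SDs, so 'conservative' may mean that the refed version was run and needed fewer subjects.

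The disclosure, the ambiguity of the rule and the consistency of the two targets all stand. They answer any suggestion that 83 is arbitrary. They do not give the primary test a power:

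- The rule allows only the SD to be updated and ties feasibility to the primary hypothesis, which is still the refed comparison.
- Matching means does not make 177 the SD of the refed difference.
- The 276 is 45% of a prior-study SD for fasting-refed differences. It is an assumption of the kind the recalculation was meant to test, and no test of it for the refed outcome is reported.
- If the refed calculation was run and was favourable, printing its SD would settle the point.

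**Conclusion.** The concern holds. The 80% at n=36 is attached to the wrong contrast, and the documents establish neither power nor feasibility for the declared primary outcome after the recalculation. This is a gap in what is shown, not evidence that the trial is too small. At the planning SD of 276 the primary test would have 87% power with 36 subjects. Power falls below 80% above an SD of about 306, and the 50-subject limit fails above about 363. These figures rest on the 147 pg/ml target, two-sided 0.05, 36 evaluable subjects and approximately normal paired differences. The prior-study SDs exceed their means (513 against 319, 1067 against 736), so skewness is likely and the figures are a guide. It should be fixed, because the power figure is wrong as attributed and the data to correct it are already held.

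**What to change.** In Section 10:

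1. From the same 17 evaluable subjects, have the statistician compute the SD of the paired NR-placebo difference in refed IL-1β and report it with its 95% CI. Releasing only the SD, not the mean difference, respects the rule against an interim efficacy look.
2. Rerun the sample size and the 50-subject check with that SD and the 147 pg/ml target. State the resulting power at 36 evaluable subjects as the trial's power, even if it is below 80%.
3. Keep refed IL-1β as the primary outcome. List fed-minus-fasting as a secondary analysis with its own power (about 78% at n=36 by paired t).
4. Describe the fasting value as on-treatment, not baseline. Remove the word 'conservative' unless the refed SD proves to be below about 313.

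The cost is one calculation from data already held and a few sentences. Reporting it needs no extra subjects. The downside is that the stated power may become less favourable, and an SD above about 363 would put the feasibility conclusion in question.
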